**Bleed Management Guidelines Day 8 and Beyond:**

When a patient experiences symptoms that may be consistent with bleeding episodes, the following steps should be followed:

1. Patient should be instructed to call the study center to discuss symptoms to determine whether or not they are consistent with a bleeding event and to discuss the appropriate factor/BPA dose to use. This interaction between patient and Investigator is recommended prior to the administration of each dose of factor or BPA. Confirmation of bleeds at the study center prior to treatment may be considered. Such visits should capture assessments per Section 6.4 and Table 2.
2. If a determination is made that symptoms require treatment, the recommended treatment algorithm for bleeding episodes is described below:
  1. A single dose can be administered according to the guidelines in Table 4.
  2. The patient should be instructed to re-evaluate symptoms in 24 hours for bleeds treated with FVIII, FIX or aPCC and in 2-3 hours for bleeds treated with rFVIIa.
    - a. Administration of FIX Extended half-life should not be more frequent than every 5-7 days.
  3. If a second dose (in the case of FVIII, FIX or aPCC) or a third dose (in the case of rFVIIa) is needed, the patient must call the study center before dosing.
    - a. Consider evaluation and treatment of the patient at the study center and confirmation of bleeds when any repeated doses are needed (See Section 6.4 and Table 2).
    - b. If more than two doses of FVIII, FIX or aPCC or three doses of rFVIIa are needed, the patient should be seen at the study center within 48-72 hours.
  4. Doses should not be administered at less than 24 hour intervals (except rFVIIa as indicated in Table 4).

5. Doses should not exceed the protocol maximum recommended dose indicated in [Table 4](#).
6. Consultation with the study Medical Monitor and Clinical Advisor should be considered for clinical circumstances below, that may warrant AT replacement:
  - a. Doses of factor or BPA higher than those recommended in [Table 4](#)
  - b. Dosing of factor or BPA at decreased intervals than those recommended in [Table 4](#)
  - c. Multiple or repeated doses of factor or BPA
7. Antifibrinolytics may not be used in combination with factor or BPA.

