### 6.3.1.3. Bleeding Episode Management Following Discontinuation of Fitusiran

Patients who opt to discontinue fitusiran may resume standard on-demand dosing with BPAs when their AT residual activity level returns to approximately 60% (per the central laboratory). An earlier restart of standard treatment may be considered in conjunction with consultation from the study Medical Monitor, if a strong medical need arises (eg, increased frequency of bleeding). If full doses of factor or BPA are required to achieve hemostasis prior to full AT recovery (approximately 60% residual activity per the central laboratory), AT replacement should be considered.

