5 GENERAL STATISTICAL METHODS

5.1 Sample Size Justification

Assuming a mean ABR of 18 with standard deviation (SD) = 14 in the on-demand arm (patients randomized to receive on-demand bypassing agents) and a mean ABR of no more than 4 with SD = 6 in the fitusiran treatment arm (patients randomized to receive fitusiran) in either the efficacy period or treatment period, with a sample size of 14 evaluable patients in on-demand arm and approximately 28 evaluable patients in the fitusiran treatment arm, it is projected that the study will have greater than 90% power for testing treatment difference in mean ABRs. This power estimation was based on negative binomial regression model with a 2-sided type I error rate of 0.05.

The planned sample size is 54 randomized patients assuming a 20% drop-out rate.

In the China Addendum #1 to protocol amendment 2, it specifies that before any Chinese patients are randomized to receive 80 mg of fitusiran subcutaneous (SC) treatment, three (3) subjects in China will be enrolled into a China specific non-randomized fitusiran treatment arm to receive fitusiran as a SC injection administered every 4 weeks, with initial starting dose of 50 mg SC. After the observation period for these 3 patients is completed and dose escalation is authorized by the Sponsor, the 3 patients will undergo dose escalation to receive 80 mg of fitusiran as a SC injection every 4 weeks. These 3 patients will not be included in the ITT Set for the efficacy analyses but will be included in the Safety Set for the safety analyses. Their efficacy data will be included in separate listings.

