Efficacy Period	Day 29 to the earliest of (Day 246, or the last day of bleeding follow up)
Treatment Period	Onset period plus the efficacy period

The last day of bleeding follow up is defined as the deactivation date captured in eDiary.

If a patient does not have bleeding episode data collected after Day 28 due to early study discontinuation, the efficacy period will be from Day 1 to the earlier of date of study discontinuation and the last day of bleeding follow up.

The onset period, efficacy period and treatment period also exclude the period of following intercurrent events to avoid confounding of treatment effect for the primary efficacy analysis based on On-Treatment Strategy.

- After one month (28 days) from fitusiran treatment discontinuation in the fitusiran efficacy period. Excluding bleeding data after one month from fitusiran treatment discontinuation is considered reasonable and adequate considering that fitusiran is dosed monthly and EOS is one month after last dose of fitusiran
- Perioperative period of major surgery. The perioperative period is defined as the day of the surgery through the final day on which supplemental hemostatic or antithrombotic treatments are administered as part of the perioperative treatment plan.
- Period of minor surgery is defined as the Perioperative period of surgery above or to 72 hours from the end of surgery, whichever is later.
- Period of Antithrombin treatment is defined as the first day of antithrombin treatment through the final day on which antithrombin or other anticoagulant therapies are administered plus 5 half-lives of that specific product.
- After prophylactic treatment with emicizumab, BPA or factor.

The summary statistics for number of patients who are lost-to-follow-up and who had each intercurrent event will be provided.

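### The antithrombin and surgery exclusions start on the day of the intervention, so a same-day bleed that led to it drops out of the primary count

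*SAP*

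**What the plan says.** SAP 6.3 defines the onset, efficacy and treatment periods and then removes from them the time belonging to five kinds of intercurrent event. The stated aim is to keep the treatment effect free of confounding. For antithrombin, the SAP gives a period "defined as the first day of antithrombin treatment through the final day on which antithrombin or other anticoagulant therapies are administered plus 5 half-lives" (those of the product given). For a major operation, "The perioperative period is defined as the day of the surgery through the final day on which supplemental hemostatic or antithrombotic treatments are administered" under the perioperative plan. Minor surgery has the same start and runs at least to 72 hours after the operation. Both definitions work in days and include the first day. No sentence retains the bleed that prompted the intervention. The table of windows is headed for both arms, and the antithrombin item names neither.

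Protocol 7.2 dates a bleed from its first symptoms. Protocol 8.2.5.1 excludes bleeding data during and after antithrombin administration or major surgery.

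In the fitusiran arm from Day 8, Protocol 6.3.1.2 says that consultation with the Medical Monitor and Clinical Advisor "should be considered for clinical circumstances below, that may warrant AT replacement". The circumstances are factor or BPA doses above Table 4, intervals shorter than Table 4, and multiple or repeated doses. Section 6.3.1.3 covers patients who have stopped fitusiran: "If full doses of factor or BPA are required to achieve hemostasis prior to full AT recovery", antithrombin replacement is to be considered. Sections 6.5 to 6.7 add thrombosis, surgery and sepsis, again for fitusiran patients. Section 6.3.1.1, on bleeds in the on-demand arm, has no antithrombin provision.

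SAP 6.3.1.2 adds a treatment-policy analysis that leaves out only events due to surgery, and a sensitivity analysis that includes all bleeds. It still calls the on-treatment estimand the most relevant one.

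**The concern.** An exclusion meant to prevent confounding should remove what happens because of the intervention. A bleed that began before antithrombin or surgery cannot be confounded by it. If that bleed is why the intervention was given, removing it makes the exclusion depend on the outcome: a bleed serious enough to need antithrombin or an operation on the day it starts leaves the count because it was serious. The protocol's wording does not clearly reach such a bleed. The SAP's day-inclusive start does.

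At stake are the size of the estimated fitusiran effect, the three secondary rates that use the same periods (treatment-period, spontaneous and joint), and the number of patients who appear bleed-free. For a patient with full follow-up, one bleed is worth 365.25/218 = 1.68 ABR units.

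**Working it through.** **1. The plan's own figure.** SAP 5.1 assumes a "mean ABR of 18 with standard deviation (SD) = 14 in the on-demand arm" and "a mean ABR of no more than 4 with SD = 6 in the fitusiran treatment arm", with "14 evaluable patients in on-demand arm and approximately 28 evaluable patients in the fitusiran treatment arm", and a "negative binomial regression model with a 2-sided type I error rate of 0.05". A Wald test on the log rate ratio gives:

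- CVs: 14/18 = 0.778 and 6/4 = 1.5.
- SE = sqrt(0.778²/14 + 1.5²/28) = 0.352.
- |log(4/18)| = 1.504, and 1.504/0.352 − 1.96 = 2.32, so power is 99.0%.

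A simulation of 1,500 trials with a common-dispersion negative binomial fit gives 98.3%; an unpooled difference in means gives 94.7%. All agree with the stated power above 90%. For the sample size, 42/0.8 rounds up to 53, and exact 2:1 allocation gives 36 + 18 = 54. The design figures reproduce.

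**2. How the rule acts on one bleed.** Let antithrombin or surgery fall on day D. SAP 6.3 does not repeat how a bleed is assigned to a period, so I use the onset rule in Protocol 7.2.

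| Bleed onset | Intervention | Primary count |
|---|---|---|
| Day D − 1 | Day D | counted |
| Day D, before the intervention | Day D | removed |
| Day D, after the intervention | Day D | removed (as intended) |

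**3. Size per bleed.** Day 29 to Day 246 is 218 days, or 218/365.25 = 0.597 years.

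- 28 fitusiran patients: 28 × 0.597 = 16.7 patient-years and 4 × 16.7 = about 67 expected bleeds. One bleed is 1/16.7 = 0.060 ABR units, or 1.5%.
- 36 fitusiran patients: 21.5 patient-years and about 86 bleeds. One bleed is 0.047 ABR units, or 1.2%.

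**4. Bleeds removed from the fitusiran arm only** (k is assumed; 28 patients, true ABR 4, on-demand ABR 18):

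| k removed | Fitusiran ABR | Rate ratio | Reduction |
|---|---|---|---|
| 0 | 4.00 | 0.222 | 77.8% |
| 1 | 3.94 | 0.219 | 78.1% |
| 3 | 3.82 | 0.212 | 78.8% |
| 5 | 3.70 | 0.206 | 79.4% |
| 10 | 3.40 | 0.189 | 81.1% |

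The length of the excluded period hardly matters, because its days also leave the offset. With k = 5, moving from 1 to 30 excluded days per event changes the ABR from 3.70 to 3.69. If both arms lose the same share f of bleeds, the ratio stays at 4(1 − f)/[18(1 − f)] = 0.222.

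**5. Bleeds restored** (if 4.00 is the ABR after exclusion, CV held at 1.5):

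| k restored | Fitusiran ABR | Power |
|---|---|---|
| 1 | 4.06 | 98.9% |
| 5 | 4.30 | 98.3% |
| 10 | 4.60 | 97.3% |
| 20 | 5.20 | 94.2% |

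**The case against.** The route is narrow. Onset on any earlier day is counted. For FVIII, FIX and aPCC, Protocol 6.3.1.2 and Table 4 put re-evaluation at 24 hours and repeat dosing no sooner, so antithrombin prompted by repeat doses would usually fall on a later day. Same-day use mainly needs repeated rFVIIa (2-hour interval) or departure from the guideline. Non-urgent surgery is not to be scheduled during the study. This stands, and it is why the point is small.

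The plan also has analyses that bring these bleeds back. The treatment-policy analysis counts bleeds in antithrombin periods, and a bleed that caused surgery is arguably not due to it. The all-bleeds version counts everything, and the treatment-policy analysis is repeated for the secondary rates. This stands in part. Those analyses also add back time after discontinuation and after prophylaxis, so they do not isolate this rule. The SAP promises numbers of patients with each intercurrent event, not bleeds or days removed.

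Three stronger readings are tempting.

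- A reader might infer that the rule acts only on the fitusiran arm. The text is arm-neutral. One-sidedness is a fair inference for antithrombin alone; the surgery rule and the perioperative plan cover both arms.
- A reader might infer that difficult bleeds are the main reason for antithrombin. The firmest provision is for thrombosis, where reversal is recommended (Protocol 6.5). For bleeds it is only to be considered.
- A reader might infer that running the antithrombin window on through other anticoagulants biases the comparison by arm. That asymmetry follows receipt of antithrombin: a fitusiran patient anticoagulated without it also stays in. The excluded days leave the offset, and Protocol 6.5 recommends the two treatments together. Changing that window is a debatable trade-off and is not asked for here.

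**Conclusion.** The gap is real but minor. As written, SAP 6.3 removes a treated bleed that begins on the same day as the antithrombin or surgery it led to, which goes beyond the stated purpose of the exclusion. At planning values each such bleed lowers the fitusiran ABR by about 1.2% (36 patients) or 1.5% (28). The antithrombin part would in practice fall almost only on the fitusiran arm; the surgery part affects both, and the documents do not show which arm would lose more.

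A reader might conclude that the primary test is at risk. It is not: power stays at 94.2% even with 20 bleeds restored. The exposure is a modest, outcome-dependent shift in the effect estimate.

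This rests on the planning ABRs, full 218-day follow-up and bleeds dated at first symptoms. The documents give no frequency of same-day cases, so every value of k is an assumption. Confidence is high for the reading of the text and low for how often it would matter.

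**What to change.** In SAP 6.3, state that a treated bleed is counted if its onset precedes the start of antithrombin or unplanned surgery on the same day and it led to that intervention. Its day stays in the duration, and the exclusion starts the following day. Report by arm the number of treated bleeds and of days removed under each exclusion rule.

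Protocol 8.2.5.1 also excludes data during and after major trauma, while SAP 6.3 has no trauma item. The new sentence should therefore say whether a major-trauma bleed that leads to surgery is covered.

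The cost is SAP wording, one programming rule and one table, using bleed, surgery and concomitant-medication dates already collected. The link between bleed and intervention needs a documented decision before database lock. The downside is that the fitusiran ABR may become slightly less favourable.

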6.3.1 Primary Endpoint

6.3.1.1 Primary Efficacy Analysis based on On-Treatment Strategy

The primary objective of this study is to assess the efficacy of fitusiran in the prevention or reduction of bleeding. Including bleeding events in the period of intercurrent events such as use of prophylactic medication or surgery or after fitusiran treatment discontinuation could significantly bias fitusiran effect and make the comparisons difficult to interpret. The on-treatment strategy is considered of greatest relevance in assessing this primary objective (ICH E9 (R1), 2018). The primary efficacy analysis population will be the ITT Analysis Set as defined in [Section 4](#).

Global Protocol

The number of bleeding episodes will be annualized for each patient using the following formula:

$$\text{Annualized bleeding rate (ABR)} = \frac{\text{total number of bleeding episodes}}{\text{total number of days in the respective period}} \times 365.25.$$

The primary efficacy analysis will include all bleeding episodes occurring in the efficacy period.

Let λ_F represent the ABR for fitusiran arm and λ_O represent the ABR for on-demand arm. The null and alternative hypotheses of the primary analysis, respectively, can be written as follows:

$$H_0: \frac{\lambda_F}{\lambda_O} = 1 \qquad H_A: \frac{\lambda_F}{\lambda_O} \neq 1$$

An estimated ABR ratio $\frac{\lambda_F}{\lambda_O} < 1$ and two-sided p-value < 0.05 from the significance test will lead to the rejection of H_0 in favor of H_A ; it will be concluded that prophylactic use of fitusiran reduces the frequency of bleeding episodes compared to the on-demand therapy.

The ABR ratio λ_F/λ_O will be estimated using a negative binomial model:

$$\log(\text{number of bleeding episodes}) = \beta_0 + \beta_1 \cdot \text{Treatment} + \beta_2 \cdot \text{ABR}_0 + \log(\text{duration}).$$

The number of bleeding episodes is the response variable. The treatment arm and the randomization strata of number of bleeding episodes in the 6 months prior to study entry (ABR_0) are treated as fixed effects. The logarithm of the duration (in years) that each patient spends in the efficacy period matching the bleeding episode data being analyzed is included as an offset variable to account for unequal follow-up time due to early withdrawal, surgery, etc.

The ratio of ABR in the fitusiran treatment arm to the on-demand arm, its 95% CI, and the p-value for the hypothesis above will be presented. The estimated mean ABRs in the 2 treatment arms along with their 95% CIs from the model will be presented. In addition, median and interquartile range (Q1, Q3) for the observed ABR will be summarized descriptively by treatment arm.

For patients who don't have bleeding episode data collected after Day 28 (eg, due to early study discontinuation), the available bleeding episode data starting from Day 1 will be used in the primary analysis. A summary of missing data pattern by treatment arm will be provided. To evaluate the impact from this single imputation, a sensitivity analysis will be performed based on imputed bleeding data in the efficacy period using multiple imputation (MI) method as described in [Section 6.3.1.2](#) below.

US Protocol

The number of bleeding episodes will be annualized for each patient using the following formula:

$$\text{Annualized bleeding rate (ABR)} = \frac{\text{total number of bleeding episodes}}{\text{total number of days in the respective period}} \times 365.25.$$

The primary efficacy analysis will include all bleeding episodes occurring in the treatment period.

Let λ_F represent the ABR for fitusiran arm and λ_O represent the ABR for on-demand arm. The null and alternative hypotheses of the primary analysis, respectively, can be written as follows:

$$H_0: \frac{\lambda_F}{\lambda_O} = 1 \quad H_A: \frac{\lambda_F}{\lambda_O} \neq 1$$

An estimated ABR ratio $\frac{\lambda_F}{\lambda_O} < 1$ and two-sided p-value < 0.05 from the significance test will lead to the rejection of H_0 in favor of H_A ; it will be concluded that prophylactic use of fitusiran reduces the frequency of bleeding episodes compared to the on-demand therapy.

The ABR ratio λ_F/λ_O will be estimated using a negative binomial model:

$$\log(\text{number of bleeding episodes}) = \beta_0 + \beta_1 \cdot \text{Treatment} + \beta_2 \cdot \text{ABR}_0 + \log(\text{duration}).$$

The number of bleeding episodes is the response variable. The treatment arm and the randomization strata of number of bleeding episodes in the 6 months prior to study entry (ABR_0) are treated as fixed effects. The logarithm of the duration (in years) that each patient spends in the treatment period matching the bleeding episode data being analyzed will be included as an offset variable to account for unequal follow-up time due to early withdrawal, surgery, or etc.

The ratio of ABR in the fitusiran treatment arm to the on-demand arm, its 95% CI, and the p-value for the hypothesis above will be presented. The estimated mean ABRs in the 2 treatment arms along with their 95% CIs from the model will be presented. In addition, median and interquartile range (Q1, Q3) for the observed ABR will be summarized descriptively by treatment arm.

Given that the primary analysis is based on on-treatment strategy, primary and secondary bleeding-related data during the efficacy and treatment periods are expected to be complete. No sensitivity analysis about the missing data mechanism will be performed.

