##### 8.2.5.1. Primary Endpoint

The primary analysis will be performed on the ITT Analysis Set and will include all bleeding episodes occurring in the efficacy period (Day 29 to Day 246) including bleeding episode data collected after discontinuation of IMP. If a patient does not have bleeding episode data collected after Day 28 (eg, due to early study discontinuation), the available bleeding episode data starting from Day 1 will be used as bleeding episode data of the fitusiran period in the primary analysis. To avoid confounding the treatment effect, bleeding episode data during and after major surgery, AT administration, major trauma, or initiation of prophylaxis treatment with BPAs will be excluded from the primary analysis.

The number of bleeding episodes will be analyzed using a negative binomial model with fixed effects of treatment arm and the number of bleeding episodes in the 6 months prior to study entry ( $\leq 10$  vs  $> 10$ ). The logarithm number of days that each patient spends in the efficacy period matching the bleeding episode data being analyzed will be included as an offset variable to account for unequal follow-up time due to early withdrawal or surgery. The p-value comparing bleeding rates in the 2 treatment arms and the ratio of bleeding rates in the fitusiran treatment arm to the on-demand arm along with its 95% CI will be presented. The estimated mean ABRs in 2 treatment arms along with their 95% CIs will be presented from this model. In addition, summary statistics for ABR, including the median and interquartile range, will be presented for each treatment arm, where ABR is defined as:

$$\frac{\text{total number of qualifying bleeding episodes}}{\text{total number of days in the respective period}} \times 365.25$$

---

Patients who discontinue treatment during the study will be encouraged to continue recording bleeding episode data.

Sensitivity analyses will be performed to evaluate the impact of missing data under different missing data mechanisms and details will be specified in the statistical analysis plan.

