6.3.1.2 Efficacy Analysis based on Treatment Policy Strategy

A supportive efficacy analysis will be performed by including all bleeding episodes collected through the end of the study, regardless of any premature treatment discontinuation, excluding only events due to major or minor surgeries based on ITT Analysis Set as in the primary analysis. The same negative binomial model as in the primary analysis will be used. It assesses the benefits of the fitusiran treatment policy strategy relative to on-demand treatment.

A sensitivity analysis to the above treatment policy analysis will be performed by including all bleeding events (ie, not excluding bleeding events due to surgeries).

Missing data sensitivity analyses using controlled imputation

The above efficacy analysis assumes the uncollected bleeding events after study discontinuation are missing at random (MAR). Sensitivity analyses will be performed to assess the robustness of this treatment policy analysis by imputing the missing data based on different missing data mechanism. The missing data will be imputed using multiple imputation (MI) methods for recurrent event data based on pattern mixture models (Keene et al, 2014) to assess the impact of different assumptions about the statistical behavior of post-withdrawal outcomes. The

post-withdrawal part of each pattern-specific distribution will be modelled using MAR and Copy Reference (CR) approaches. The MI will be carried out in the following steps:

1. Fit a Bayesian negative binomial model with a non-informative prior to the observed data with same set of covariates as in the primary analysis and obtain the posterior distributions of the event rate for both treatment arms.
2. Draw 100 independent samples from the conditional distribution of missing counts given the observed count and period of each patient with missing data based on different post-withdrawal imputation models, described below, for the treatment arms. The conditional distribution is also negative binomial.
3. The observed counts and imputed counts for each patient with missing data are summed.

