4. Each 100 imputed datasets will then be analyzed using the same negative binomial regression model. Estimates from the model such as least squares means and standard errors are then combined across imputation datasets using Rubin's formula, as implemented in the MIANALYZE procedure. These and their 95% confidence interval limits are then exponentiated to obtain the estimate of ABR for each arm and the estimate of the ABR ratio and associated p-value.

MAR and CR approaches are described below:

1. Missing at Random (MAR) Approach: Post-withdrawal missing bleeding events in both fitusiran arm and on-demand arm will be imputed under the randomized arm.
2. Copy Reference (CR) Approach: The expected ABR for a patient in the fitusiran arm both pre- and post-withdrawal is assumed to be the same as that in the on-demand arm. This accounts for a gradual loss of fitusiran effectiveness post-withdrawal. If a patient in fitusiran arm has more events pre-withdrawal than expected if this patient had been in the on-demand arm, then this 'positive residual' will feed through into a higher than expected ABR in the post-withdrawal period. This is because this patient's earlier observed ABR higher than mean event rate suggests the patient has a higher propensity to have events. Post-withdrawal data in the on-demand arm are imputed under randomized arm (assumes MAR approach).

The efficacy analysis based on treatment policy strategy may serve as sensitivity analyses for the primary efficacy analysis based on on-treatment strategy. It is important to note that the estimand based on on-treatment strategy (the primary efficacy analysis) is considered most relevant and applicable in assessing and reporting clinical efficacy of fitusiran vs. on demand treatment.

Per-protocol analysis

Efficacy analysis will be repeated on the per-protocol analysis set as defined in [Section 4](#).

Zero-inflated negative binomial model

To address the concern of potential excessive zero bleeding events, the above on-treatment and treatment policy efficacy analyses will be repeated using the zero-inflated negative binomial model and the results will be presented if model converges.

Covid-19 related sensitivity analysis

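### Under the plan's own SDs, a single-dispersion negative binomial model gives a nominal 95% interval for the fitusiran mean ABR that covers about 85–87%, and an on-demand interval that covers about 98%

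*SAP*

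**What the plan says.** SAP 6.3.1.1 specifies a negative binomial model whose fixed effects are "The treatment arm and the randomization strata of number of bleeding episodes in the 6 months prior to study entry", with log duration as offset. The arm means come from the same fit: "The estimated mean ABRs in the 2 treatment arms along with their 95% CIs from the model will be presented". The Global and US texts both say this, and Protocol 8.2.5.1 agrees: "The estimated mean ABRs in 2 treatment arms along with their 95% CIs will be presented from this model".

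Neither document says how dispersion is parameterised. Robust variance is named only for the Cox model in SAP 6.3.1.3.

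The supportive analyses inherit the specification. For treatment policy, SAP 6.3.1.2 says: "The same negative binomial model as in the primary analysis will be used". For multiple imputation: "Estimates from the model such as least squares means and standard errors are then combined across imputation datasets".

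The sample size in SAP 5.1 (and Protocol 8.1) rests on "Assuming a mean ABR of 18 with standard deviation (SD) = 14 in the on-demand arm" and "a mean ABR of no more than 4 with SD = 6 in the fitusiran treatment arm".

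**The concern.** The planning values describe two arms with very different relative spread: SD/mean is 14/18 = 0.78 on-demand and 6/4 = 1.5 on fitusiran. A model with one dispersion parameter cannot represent both. It averages them, so the standard error of the fitusiran log mean is too small and that of the on-demand log mean is too large.

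The mean ABR per arm with its 95% CI is a named output of the primary analysis. If the planning SDs hold, its stated precision is wrong in opposite directions in the two arms, and the overstatement falls on the investigational arm.

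**Working it through.** **Inputs.** Means and SDs as above. Sample sizes are written on-demand/fitusiran: 14/28 evaluable (SAP 5.1) and 18/36 randomised (Protocol 1.3). The efficacy period, Day 29 to Day 246, is 218 days (SAP 6.3), so t = 218/365.25 = 0.597 year.

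**1. Dispersion implied by each arm.** k = (SD² − mean/t)/mean².
- On-demand: (196 − 18/0.597)/324 = 0.51
- Fitusiran: (36 − 4/0.597)/16 = 1.83

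The ratio is 1.83/0.51 = 3.6. Over the 246-day treatment period the values are 0.52 and 1.88.

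**2. The plan's own figure.** The variance of the log rate ratio at 14/28 is (1/(18t) + 0.512)/14 + (1/(4t) + 1.831)/28 = 0.605/14 + 2.250/28 = 0.1236, so SE = 0.3515. Then ln(18/4)/SE − 1.96 = 1.504/0.3515 − 1.96 = 2.32, and power is 99.0%. Simulated power with the shared-dispersion analysis is 98.4–99.7%. The stated power of more than 90% reproduces.

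**3. Effect of sharing k, by hand at 18/36.** The variance of an arm's log mean is (1/(mean·t) + k)/n.
- Fitusiran: √((0.419 + 1.831)/36) = 0.250 with its own k; √((0.419 + 0.95)/36) = 0.195 with the shared k of about 0.95.
- On-demand: √((0.093 + 0.512)/18) = 0.183 with its own k; √((0.093 + 0.95)/18) = 0.241 with the shared k.

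**4. Simulation of the full model.** There were 4,000 gamma-Poisson trials per scenario. Each was fitted by maximum likelihood with treatment, stratum (50:50 split assumed) and offset, with Wald limits for the least squares means on the log scale. Monte Carlo error near 87% is √(0.87·0.13/4000) = 0.5 points. At 18/36 the model SE against the true SE is 0.198 against 0.255 (fitusiran) and 0.243 against 0.189 (on-demand).

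| Scenario, shared dispersion | Fitusiran | On-demand |
|---|---|---|
| Efficacy period, 18/36 | 86.9% | 98.5% |
| Efficacy period, 14/28 | 85.2% | 97.7% |
| Stratum rate ratio 2, 18/36 | 86.7% | 98.4% |
| Stratum rate ratio 2, 14/28 | 85.3% | 98.3% |

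Fitusiran coverage in the treatment period is 86.0% (18/36) and 85.5% (14/28). With 20% dropout at 18/36 it is 86.8%. Smaller repeat runs (800 to 2,500 trials per cell) give 84.4–87.8% for fitusiran and 97.1–98.7% for on-demand. Coverage of the ratio's CI is 92.4–94.6% across the planning-SD scenarios.

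**5. Dependence on the planning SDs** (fitusiran coverage).

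| Assumption | 18/36 | 14/28 |
|---|---|---|
| Planning SDs (3.6-fold) | 86.9% | 85.2% |
| Dispersion ratio 2 | 91.5% | 90.2% |
| Dispersion ratio 1.5 | 92.4% | 92.2% |
| Equal dispersions | 93.3% | 94.1% |
| Fitusiran mean 2, SD 3 (assumed) | 89.4% | 89.0% |

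**6. What the reader would see at 18/36**, as estimate × exp(±1.96·SE).
- Fitusiran at 4: 2.7 to 5.9 with SE 0.198; 2.4 to 6.6 with SE 0.255.
- On-demand at 18: 11.2 to 29.0 with SE 0.243; 12.4 to 26.1 with SE 0.189.

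**The case against.** - **No decision uses these intervals.** The hypothesis test and hierarchy rest on the ratio, and the SAP also reports each arm's observed median and quartiles. This stands and limits the importance of the point. It does not make the intervals right.
- **The SAP is silent on dispersion; it does not choose a shared one.** True. The finding rests on the ordinary default. If the sponsor meant something else, the SAP still needs to say so.
- **The planning values are cautious.** The fitusiran mean is an upper bound, and Protocol 1.2.2.1 reports a median ABR of 0 in 11 inhibitor patients on 80 mg. This stands: smaller dispersion ratios shrink the problem, as step 5 shows, and one to two points of the shortfall are ordinary small-sample behaviour.
- **Excess zeros.** SAP 6.3.1.2 plans a zero-inflated model because of this possibility, without stating whether variance may differ by arm. With 40% structural zeros and the same mean and SD, the shared model covers 89.0% (18/36) and 86.0% (14/28), and the replacement proposed below covers 97.0% in both. With 55% zeros at 18/36 the figures are 90.9% and 99.0%. The undercoverage remains, but the replacement turns conservative, and at 55% it is about as far from nominal as the planned interval. This is a real limit of the remedy.
- **Two models in one table.** This also stands; it is a cost of the remedy.

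**Conclusion.** The concern holds. If the planning SDs are right and one dispersion is fitted, the nominal 95% interval for the fitusiran mean ABR covers about 85–87% and the on-demand interval about 98%, in both sample-size scenarios. With equal dispersions the fitusiran figure returns to 93–94%, so unequal dispersion is the cause. None of the supportive analyses clearly corrects it.

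The result rests on the default reading of the model, gamma-Poisson counts and the planning SDs. It applies to overall ABR in the efficacy and treatment periods. The spontaneous, joint and onset rates use the same model, but the documents give no SDs for them. The primary conclusion is not threatened. This is an error in the stated precision of a reported primary result, and it should be corrected before database lock. Confidence is medium, because the observed dispersions may differ from the planned ones.

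**What to change.** Keep the planned model for the ratio, its CI and the p-value. In both the Global and US text of SAP 6.3.1.1:

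- Take each arm's mean ABR and 95% CI from one joint negative binomial fit with the same treatment effect, common stratum effect and offset, but a separate dispersion per arm (for example in PROC NLMIXED). Separate fits per arm should not be used; they would lose the common stratum effect.
- Use t-based limits on the log scale with n − 1 degrees of freedom for the arm. This is a pragmatic choice supported by simulation.
- State a fallback to the planned limits if the fit does not converge, and record the change in SAP 2.6.

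Under the planning values, coverage is then 94.4% fitusiran and 93.4% on-demand at 18/36, and 93.6% and 93.0% at 14/28. With a stratum rate ratio of 2 it is 94.6% and 93.7%, and 93.6% and 93.7%. Wald limits from the same fit would leave on-demand at 91.4% and 90.8%.

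A sandwich variance from the planned fit with the same t limits covers 92.7–95.2%. It is an acceptable, simpler route that keeps the arm means consistent with the ratio.

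The cost is SAP wording and a short program. The fitusiran interval widens. With the joint fit the two means may not divide exactly to the reported ratio (median gap about 1%; 90th percentile 6% at 18/36 and 8% at 14/28), so the table needs a footnote. Slight undercoverage remains under the planning values, and the limits become conservative if there are many structural zeros.
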